4. SUBJECT SELECTION CRITERIA

The Investigator should keep a record (i.e., screening log) of subjects who were screened.

Each subject must meet all the inclusion criteria and none of the exclusion criteria for this study at the time of randomization. Under no circumstances can there be exceptions to this rule. A repeat test may be allowed in the screening period with the Sponsor's medical monitor approval, with the exception of the AISRS and CGI-S, which can only be assessed once at screening for eligibility purpose.

4.1 Inclusion Criteria

All inclusion criteria will be based on the medical judgment of the Investigator. For inclusion in the study, subjects must meet all the following criteria:

1. Ability and willingness to provide written, informed consent prior to initiation of any study-related procedures and to adhere to all study requirements.
NOTE: The subject (i.e., not a legally authorized representative) must be cognitively able to understand the requirements of the study and provide the informed consent.
2. **Age ≥ 18 and ≤ 65 years at Screening.**
3. Subjects with the diagnosis of Diagnostic and Statistical Manual of Mental Disorders-5 (DSM-5) ADHD, as determined by clinical evaluation and confirmed by structured interview (MINI).
4. **AISRS total score of ≥ 26 at screening.**
5. **CGI-S score of ≥ 4 at screening.**
6. Must be willing to receive IMP dose twice weekly. On Day 1, the subject will come to the clinic and must be willing to take a taxi or public transportation home or be accompanied by a caregiver and not drive a car, use heavy equipment, or participate in any other dangerous activity for the remainder of the day after receiving IMP (NOTE: at any protocol visit after Day 1 dosing, dosing visits may occur at the subject's home at the discretion of the PI, conducted by one of the study investigators or delegate and administered under supervision followed by the performance of the same procedures done at the clinic including safety monitoring. If early withdrawal is considered due to any safety issue identified, the Sponsor's medical monitor should be notified. If a remote visit is conducted due to any reason related to the COVID-19 pandemic, notification must be sent to the Medical Monitor's dedicated email address and Urgent Safety Measures as outlined in this protocol must be followed.)
7. Must be willing to refrain from more than 6 standard alcoholic drinks per week (1 standard drink corresponds to 0.1 L wine, 0.3 L beer, or 4 cL liquor), more than 10 cigarettes a day, and more than 2 cups of coffee a day throughout the study treatment period (6 weeks) and until the last study visit is complete (EoS or ET).

4.2 Exclusion Criteria

Subjects should not be included in the study if any of the following exclusion criteria are met:

1. Past or present diagnosis of a primary psychotic disorder or first-degree relative with a psychotic disorder.
2. Past or present bipolar disorder (DSM-5).
3. Other current psychiatric disorders that, in the opinion of the Investigator or medical supervisor, may confound the results of the study (e.g., obsessive-compulsive disorder, dysthymic disorder, panic disorder, dissociative disorder, anorexia nervosa or bulimia nervosa).
4. Subjects with [REDACTED] substance use disorder (except nicotine, provided subject does not smoke more than [REDACTED] a day).
5. Somatic disorders including Central Nervous System (CNS) involvement of cancer, severe cardiovascular disease, untreated hypertension, severe liver disease (liver

enzyme increase by more than 3x the upper limit of normal except unconjugated hyperbilirubinemia due to Gilbert's Disease, per Investigator), severely impaired renal function (estimated creatinine clearance < 50 mL/min by CKD-EPI formula), or anything else that, in the judgment of the Investigator or medical supervisor, poses too great a potential for side effects.

6. Any lifetime history of suicide attempt; [REDACTED]
[REDACTED] suicidal thoughts or ideation (defined as a suicidal ideation score of 2 or greater in the Columbia-Suicide Severity Rating Scale [C-SSRS]); or endorsement of any suicidal behavior on the C-SSRS within [REDACTED] the screening visit.
7. Likely to require psychiatric hospitalization during the course of the study.
8. Once consent is signed, subject not willing or able to stop any prescription or non-prescription ADHD medications during screening and prior to the baseline visit through final study visit (EoS or ET). *A list of prohibited medications is provided in Appendix 1.*
9. Plan to start, stop, or alter the use of any medications, supplements, or other therapeutics from Baseline until EoS or ET (see Appendix 1 for list of prohibited medications).
10. Plan to start, stop or alter the use of psychotherapy, massage, meditation, acupuncture, hypnosis, yoga, or other similar therapy/activity from the time of providing informed consent until EoS or ET.
11. [REDACTED]
[REDACTED]
12. Likely to need use of any psychiatric medications with the potential to confound interpretation of study results or impact safety, at the discretion of the Investigator, in the 10 weeks following Baseline up to EoS or ET (see Appendix 1 for list of prohibited medications).
13. Use of investigational medication/treatment in the past 30 days prior to the screening visit.
14. [REDACTED]
[REDACTED]
15. Clinically significant abnormal baseline laboratory values, VSs, and ECG that include the following:
 - a. Have evidence of clinically significant hepatic disorder (e.g., alanine aminotransferase [ALT] or aspartate aminotransferase [AST] > 3X ULN (except for Gilbert's disease), and
 - b. Any clinically significant abnormal metabolic or hematologic screen, per Investigator or medical supervisor decision
 - c. Exclusionary blood pressure: >140 mm Hg (systolic) or >90 mm Hg (diastolic); heart rate <45 beats/minute or >90 beats/minute after an approximately 5-minute supine or semi-supine rest
NOTE: If the first measurement of a subject's heart rate is > 90 beats/minute, a second recording is allowed after an additional approximately 5-minute supine rest
 - d. Exclusionary ECG parameters: QTcF > 450 msec (men), QTcF >470 msec (women)
 - e. Any clinically significant abnormal electrocardiogram (ECG) finding (e.g., uncontrolled atrial fibrillation, ischemia) at Screening (Visit 1) or Baseline

(Visit 2), as determined by the Investigator or medical supervisor (in consultation with a cardiologist, if needed).

16. Any other condition, therapy, laboratory abnormality, or other circumstance that, in the opinion of the Investigator or medical supervisor, may pose additional risk to the subject from participation in the study, may interfere with the subject's ability to comply with study procedures, may make participation in the study not in the subject's best interest or may confound the results of the study.
17. Prior history or ongoing neuropsychiatric signs or symptoms associated with COVID-19 such as development of, or current disorder, during or after a COVID-19 infection including anxiety, memory loss, confusion, depression, delirium, agitation, or psychosis.
18. Women of childbearing potential (WOCBP) (i.e., physiologically capable of becoming pregnant) who are unwilling or unable to use a highly effective method of contraception, as defined in Appendix 2, for the duration of the study, OR Men physiologically capable of fathering a child who are sexually active with WOCBP but are unwilling or unable to use barrier contraception (e.g., condom with or without spermicidal cream or jelly) for the duration of the study.

NOTE: See Appendix 2 for definitions of WOCBP and highly effective methods of contraception and for information about unacceptable methods of contraception.

19. Women who are currently pregnant or breastfeeding or plan to become pregnant or breastfeed during the study.
20. Men who plan to donate sperm during the study.
21. Use of weight loss drugs [REDACTED] until the end of study.
22. Subjects who are either unable or unwilling to consume alcohol in any amount (including due to religious or personal reasons).
23. Subjects who have a change in AISRS score of ≥ 13 -points between screening and baseline visits.

5. STUDY CONDUCT

5.1 Subject Enrolment and Randomization

The Investigator will ensure:

- Signed informed consent is obtained from each potential subject before any study specific procedures are performed.
- The eligibility of each subject is determined, as described in Sections 4.1 and 4.2, before administering any IMP.

Each screened subject will be identifiable by a unique screening number. The randomization number will be assigned to the subject on Day 1 before first dosing.

This will be a double-blind study, with the random code generated by the study biostatistician, and provided to the GMP facility for packaging. The subject and Investigator will remain blinded to treatment assignment until the conclusion of the study unless it necessary to unblind the data for safety reasons. Only the GMP facility producing the IMP and the Principal Investigator (PI) at each site have access to the code (sealed envelopes). In case of a medical emergency, and in case of premature study termination, the code can be accessed by the PI.

In case of an emergency requiring immediate knowledge of the study treatment and appropriate management of the subject requires knowledge of treatment randomization, the treatment code may be broken by the Investigator. The Investigator should discuss the case with the Sponsor's Medical Monitor immediately after breaking the treatment code.

The Sponsor's unblinded personnel may unblind treatment assignment for an individual subject's SAE in order to fulfill expedited regulatory requirements.

Changes that may be implemented, if needed, due to the coronavirus disease 2019 (COVID-19) pandemic are described in Section 7.11 and a detailed impact will be included in the clinical study report (CSR).

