3. STUDY PLAN AND PROCEDURES

3.1 Overall Study Design

This study is a multi-center, randomized, double-blind, placebo-controlled Phase 2a study of low dose MM-120 (20 µg) compared with a placebo administered for 6 weeks (twice a week).

There will be a 1:1 randomization, double-blind, to MM-120 or placebo of 52 adults with ADHD with the aim to reach 26 evaluable subjects in each of the 2 arms at Week 6.

There will be 2 arms:

- Arm 1-Placebo: a total of 26 subjects will receive a placebo identical in appearance to the IMP administered orally twice weekly for 6 weeks. Subjects and site staff will remain blinded to the treatment arm.
- Arm 2-MM-120: a total of 26 subjects will receive 20 µg of MM-120 twice weekly for 6 weeks. Subjects and site staff will remain blinded to the treatment arm.

Subjects will be evaluated at Baseline, Week 1, Week 6, and Week 10 (follow-up) for AISRS and CGIS by a trained study personnel; the primary endpoint will be based on evaluation of AISRS at Baseline and at Week 6, with a key secondary endpoint after 1 week of treatment.

Subjects are free to discontinue the study at any time without providing a reason. However, the Investigator should try to identify the reason and document in the eCRF.

Specific reasons for discontinuing from the study should be documented in the eCRF, and include, but are not limited to:

- Subject's decision
- The Investigator or Sponsor judges that it is in the best interest of the subject to stop study treatment due to any abnormality compromising subject safety
- Pregnancy
- Severe noncompliance to the study protocol as judged by the Investigator and/or the Sponsor.

Subjects who prematurely discontinue may be replaced, per Sponsor decision. Subjects will not be allowed to re-enter the study.

The study will stop enrolling subjects once 26 subjects per arm are randomized, or if the Investigator or the Sponsor judges that it is in the best interest of the subjects to stop study enrollment due to low accrual or safety or other reason. Subjects who have given informed consent and have not yet been excluded, completed, or terminated from the study will be allowed to continue in the study. An evaluable subject is defined as a randomized subject (as defined in the Statistical Analysis Plan [SAP]).

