11.2 Data Management by a Delegate

Data management will be performed by the Sponsor or its delegate. Data queries will be raised for inconsistent, impossible, or missing data. All entries to the study database will be available in an audit trail. The data will be validated as defined in the Data Management Plan. Quality control procedures will be applied to each stage of data handling to ensure that all data are reliable and have been processed correctly. When all data have been coded, validated, and locked, a clean file will be declared. Any treatment-revealing data may thereafter be added, and

the final database will be locked. Data storage will be done in accordance with GCP guidelines. The Data Management Plan will describe the methods used to collect, check, and process clinical data in detail. It will also clarify the roles and responsibilities for the different functions and personnel involved in the data management process. Furthermore, the Data Management Plan will describe the data flow and timelines within the study.

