## 8.7 TRIAL DISCONTINUATION

Subjects with premature trial termination are identified as those with answer 'No' to the question 'Did the subject complete the study?' in the “Termination Form” CRF section.

The reasons that can be associated with the trial discontinuation are:

- Lost to follow-up;
- Death;
- COVID-19 related;
- Other (to be specified).

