#### 10.7.2.1.1 *Definition of intercurrent events (IEs)*

1. IEs related to COVID-19 pandemic are confirmed if:

- AE term AEDECOD is 'SARS-CoV-2 test positive' in the sdtm database. The AE start date AESTDTC will be considered to assign missing values (as defined in bullet 1 of Section 10.7.2.2) to all assessments following this date and up to and including Week 6 D40.

2. Intake of prohibited medications/therapies defined in APPENDIX C will be finalized and flagged accordingly on a case-by-case basis by a Sponsor medical review of the concomitant medications as defined in Section 8.4.3. The CM start date will be considered to assign missing values (as defined in bullet 2 of Section 10.7.2.2) to all assessments following this date and up to and including Week 6 D40.
3. Other IEs leading to treatment/study discontinuation (except those related to COVID- 19 pandemic) are confirmed if:

the action taken AEACNOTH of the corresponding adverse event is 'DRUG DISCONTINUED' or 'SUBJECT WITHDRAWAL' in the sdtm database and subject had study assessments after the AE onset date AESTDTC and up to and including Week 6 D40.

In all cases if the date of the assessment and the IE start date occur in the same date, this assessment values will be assigned to missing.

If the date of assessments following the IE start date are missing, these will be imputed based on the theoretical date the assessments should have been occurred:

- if the IE start date <= study day 9 then both Week 2 and 6 assessments have to be set to missing and imputed
- if the IE start date is between study day 10 and 44 then Week 6 assessment has to be set to missing and imputed

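### Protocol 5.1 lets a site PI open the treatment code on premature study termination, a term it neither defines nor ties to database lock

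*Protocol*

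**What the plan says.** Protocol 5.1 places the code in sealed envelopes with the manufacturing facility and the PI at each site. The general rule is that subject and Investigator "will remain blinded to treatment assignment until the conclusion of the study unless it necessary to unblind the data for safety reasons". Shortly afterwards the section adds: "In case of a medical emergency, and in case of premature study termination, the code can be accessed by the PI". The duty to discuss a code break with the Medical Monitor is attached to emergencies only. Two other openings are provided for separately: by the sponsor's unblinded staff for expedited SAE reporting (5.1), and at the request of a pregnant subject or partner, with the study team kept blinded (14.4).

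Protocol 11.2 sets the order for the database: "When all data have been coded, validated, and locked, a clean file will be declared. Any treatment-revealing data may thereafter be added". It does not mention the site envelopes.

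Protocol 11.1.5 allows the study to be terminated for poor conduct, slow recruitment or safety concerns.

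SAP 8.7 uses a close variant of the term for individuals: "Subjects with premature trial termination are identified as those with answer" *No* to the question on study completion.

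SAP 10.7.2.1.1 recognises a discontinuation event not related to COVID-19 when "the action taken AEACNOTH of the corresponding adverse event is" either drug discontinued or subject withdrawal, with study assessments after the AE onset date.

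**The concern.** In section 5.1 the exception to blinding is safety, but the second ground for opening the code has no safety condition. A study stopped for slow recruitment meets that ground although nobody's safety requires the code. At that moment AE records, relatedness ratings and data queries at the site may still be open.

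The PI holds the envelope and answers for those records. If they are completed with the arm known, the blind no longer protects them. One part of that material, AE action taken and onset date, is read directly by the primary analysis. The rest shapes the safety tables.

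**Working it through.** No figure in either document depends on the code-access rule, so there is nothing to recompute. The check is to fix what the term means, when the code may be opened, and which site entries can then reach an analysis.

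**1. What the term covers.**

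| Place | Unit meant |
|---|---|
| Protocol 11.1.5, study termination | whole study |
| Protocol 5.3, drug return after study termination | whole study |
| Protocol 3.1.1, subject terminated for a failed or missed baseline AISRS | one subject |
| Protocol 6.2.5, early termination visit | one subject |
| SAP 8.7, premature trial termination | one subject |

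The exact noun phrase, *study termination*, refers to the whole study wherever the protocol uses it elsewhere. That is the natural reading, but no definition excludes the other.

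**2. When the code may be opened.** Section 5.1 gives no time relative to clean file or lock. Section 11.2 governs when treatment-revealing data enter the database, not when a PI may open an envelope. The permission is therefore open in time. Opening before lock follows from that silence; it is not stated.

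**3. Which entries reach which analysis.**

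| Entry | Made by | Use |
|---|---|---|
| AE action taken, AE onset date | site | Primary analysis: can define the intercurrent event and its start (SAP 10.7.2.1.1) |
| AE relatedness | Investigator (protocol 7.7) | Related-AE and SAR tables (SAP 8.11.1.4, 8.11.1.8) and SUSAR classification (protocol 7.6.5) only |
| Prohibited-medication flag | sponsor medical review | Primary analysis, but not set by the PI |
| AISRS at Week 2 and Week 6 | trained study personnel (protocol 3.1) | Primary model (SAP 10.7.2.2) |

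**4. The action-taken route.** A qualifying action code places the subject under the second policy strategy in SAP 10.7.2.1: AISRS values after the event are set to missing and imputed by reference to placebo. Without such a code, and with no prohibited medication, a missing value is imputed under MAR from the subject's own arm. The onset date fixes which visits are affected. Where assessment dates are missing, a start up to Day 9 removes Weeks 2 and 6, and a start from Day 10 to Day 44 removes Week 6 only.

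**5. The ratings route.** SAP Table 2 maps AISRS ratings from EOT+1 onward to the Week 10/final-visit window, and the primary model uses Weeks 2 and 6 only. Most exit ratings therefore cannot enter it. Two edge cases remain:

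- A rating on the last-dose day, from Day 35 on, can be the Week 6 value.
- The Week 2 window runs from Day 2 to Day 21 and overlaps EOT+1 for anyone who stops early. For a subject whose last dose is on Day 5, EOT+1 is Day 6, so an exit rating from Day 6 to Day 21 falls in both windows. The table does not say which takes precedence. If taken as Week 2, it enters the primary model and the key secondary analysis (SAP 10.8.1.1).

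The rater need not be the PI, but no separation between them is required.

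**The case against.** The other side has a good case, and much of it stands.

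- *An early stop is itself the conclusion of the study*, so the clause may only restate the general rule, and 11.2 continues to bind the database. That softens the conflict on the whole-study reading. It does not supply the missing link to lock.
- *Action taken is largely a fact.* Drug was stopped or it was not, and for an individual leaver that decision comes before the exit that would open the envelope. This stands for the decision. The entry, the onset date and query answers can still be completed later.
- *The SAP already tests the imputation choice.* Copy-reference imputation for all missing data (10.7.3.2) and a MAR run (listed in 12.4.2) do not use the action code to choose between own-arm and placebo imputation. This stands, and limits what miscoding could hide.
- *A study stopped for safety may need codes at sites.* This stands, and the fix keeps a safety exception.

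Some stronger readings are tempting but unsupported. A reader might infer that relatedness feeds the primary analysis; it does not. A reader might infer that subjects keep being treated and rated after termination, because section 3.1 says: "Subjects who have given informed consent and have not yet been excluded, completed, or terminated from the study will be allowed to continue". That sentence follows a stop of enrolment, not of the study, and the documents do not equate the two. A reader might also infer that every early leaver's code may routinely be opened. That needs the subject-level meaning, which is the less natural one.

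**Conclusion.** The point holds as a gap in the blinding rule. Section 5.1 grants site access to the code on an undefined event, with no safety condition and no tie to lock, beside a general rule whose stated exception is safety. As written, a PI may know treatment before final AE entries, relatedness ratings and query answers are complete.

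The exposure is contingent and probably small. On the whole-study reading it needs the trial to stop early and a PI to open envelopes before lock. To affect the primary estimate, it also needs a subject with a qualifying AE whose action or onset entry is still open, or one of the two rating edge cases.

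A reader might try to size the bias by assuming a dropout rate and spreading the 0.60 design effect over 26 subjects per arm. The documents do not support this. They give no dropout rate, and most leavers would not be reclassified by the action code. No bias figure can be derived from them.

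The change is still worth making: the endpoint is clinician-rated, the trial has 52 subjects and a blinded-site promise, and the correction is nearly free.

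**What to change.** Replace the clause in protocol 5.1 with three statements:

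1. Before clean file or database lock, sites open the code only for a medical emergency or other safety need. The sponsor's SAE provision in 5.1 and the pregnancy provision in 14.4 are unchanged.
2. After premature termination of the study as a whole, codes are released to sites only after lock under 11.2.
3. An individual subject's early termination is not in itself a ground for opening the code.

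If data collection has finished, the clinical study report should say whether any envelope was opened on this ground, and whether any AE action, onset or relatedness entry was made or changed afterwards.

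The cost is one replaced clause and two added sentences. Emergency and safety unblinding are not restricted, and the analysis does not change. The only operational effect is that, after a stop for reasons other than safety, sites wait for lock.
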